6.3 Discontinuation or withdrawal

List the procedures that will be performed for each subject that withdraws prior to completing the study.

6.3.1 Criteria for withdrawal from the study

In accordance with applicable regulations, a subject has the right to withdraw from the study, at any time and for any reason, without prejudice to their future medical care.

If a subject withdraws consent, the date and reason for consent withdrawal should be documented. Subject data will be included in the analysis up to the date of the withdrawal of consent.

Apart from withdrawal of consent, reasons for early termination of individual subjects may include:

- Protocol deviations or subject non-compliance (must be specified on the appropriate CRF)
- Adverse events
- The Investigator considers that it is in the subject's best interest to discontinue their participation in the study
- Subject is lost to follow-up
- Other (must be specified)

In case of discontinuation without withdrawal of informed consent, survival data will be collected at the remaining follow-up timepoints (i.e. 1m +/- 1 week, 3m +/- 3 weeks , 6m +/- 3 weeks, 12m +/- 3 weeks, 18m +/- 3 weeks and 24m +/- 3 weeks after randomization date) and the occurrence of an SSE will be registered in the eCRF if it occurs within 24m after the randomization date.

If a subject is withdrawn because of an AE, the Investigator should follow each AE until the event has resolved to baseline grade or better, the event is assessed as stable by the Investigator, the subject is lost to follow-up, or the subject withdraws consent. Every effort should be made to follow all serious adverse events (SAE) considered to be related to study treatment or trial-related procedures until a final outcome can be reported.

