- j. For each SAE, it should be evaluated whether it concerns an SSE. If it concerns an SSE, the SAE should be documented as such in the eCRF and the necessary actions should be taken (see footnote h). In case hospitalization occurs, it should be evaluated whether the hospitalization is related to the high-risk metastase(s) and this information should be documented in the eCRF. Note that only (S)AE related to the bone metastatic disease or related to radiotherapy (only applicable for arm B) must be reported in the eCRF and that all SSE need to be registered in both study arms, including an SSE in a bone metastasis that was not previously included in the study (only applicable for arm B). An exception are SSE's in bone metastases that were already treated with surgery or RT before study participation.
- k. In case of discontinuation of a subject's participation without withdrawal of consent, only survival data will be collected at the remaining follow-up timepoints (i.e. 1m, 3m, 6m, 12m, 18m and 24m after randomization date) and the occurrence of an SSE will be registered in the eCRF if it occurs within 24m after the randomization date.
- l. Patients in the upfront RT arm developing new minimally symptomatic or asymptomatic high-risk bone metastases during study participation are strongly advised to further be treated with preventive RT. Details concerning the characteristics of these new high-risk metastases as well as details regarding the preventive RT must be captured in the eCRF.

Clinical Trials Oncology

Ref.Nr.: P.01-S.23

Versie: 6.0

Administrative structure

Study responsible physician:	[name] Iridium Netwerk Department of Radiation Oncology [name]
Project managers:	Clinical Trials Office (CTO), Oncologisch Centrum ZAS [contact], [contact] [contact] www.clinicaltrials oncology.be
Sponsor	ZAS vzw, [name] [contact] www.zas.be

1. Background & Rationale

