8.2.2 Period for collecting AE and SAE information

During the period from main ICF signing to the last follow-up visit (24m after randomization date), date of death of any cause or early end of participation in the study due to other reasons, all (S)AE that are related to the bone metastatic disease or related to radiotherapy (only applicable for patients in arm B) will be documented in both study arms.

The following applies for (S)AE related to RT (arm B):

Toxicity that appears within 90 days after the last RT dose will be regarded as acute toxicity.

Toxicity that appears >90 days after the last RT dose administration will be regarded as late toxicity.

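### Ending participation for non-compliance, a protocol deviation or an adverse event stops quality-of-life, new-toxicity and hospitalization data in patients who still consent

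*Protocol*

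**What the plan says.** Section 6.3.1 opens its list with "Apart from withdrawal of consent, reasons for early termination of individual subjects may include". The list includes "Protocol deviations or subject non-compliance (must be specified on the appropriate CRF"), adverse events, the investigator's view of the patient's best interest, loss to follow-up, and other reasons.

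Footnote k of Table 1 says what follows: "In case of discontinuation of a subject's participation without withdrawal of consent, only survival data will be collected at the remaining follow-up timepoints". Both footnote k and section 6.3.1 add that "the occurrence of an SSE will be registered in the eCRF if it occurs within 24m after the randomization date".

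Section 8.2.2 runs adverse-event collection from consent to the 24-month visit, "date of death of any cause or early end of participation in the study due to other reasons". Table 2 and section 9.3 give the same end point for adverse events and for hospitalizations, and footnote i of Table 1 repeats it for hospitalizations.

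Section 6.3, where the procedures at exit should stand, holds an unfilled template instruction: "List the procedures that will be performed for each subject that withdraws prior to completing the study".

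Section 9.2 states that patients are analysed by their randomised arm.

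**The concern.** Study treatment is over within weeks of randomisation, while follow-up lasts 24 months. A deviation from treatment, poor compliance or an adverse event is no reason to stop observing a patient who still consents. Yet section 6.3.1 allows each of these to end participation, and the other provisions then switch off three of the four secondary outcomes: quality of life, toxicity and hospitalizations.

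The loss is unlikely to be random, because these exits are defined by how the patient tolerated or adhered to the plan, and the decision lies with sites that know the arm. Section 9.2 promises a comparison as randomised, but for these outcomes such patients would have nothing to contribute after exit. A later analysis plan can model missing data; it cannot bring back observations that the protocol told sites not to make.

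**Working it through.** **1. What survives an exit without withdrawal of consent**

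| Outcome | Where stated | After exit |
|---|---|---|
| SSE | 6.3.1, footnote k | registered to 24 months |
| Overall survival | 6.3.1, footnote k | collected at remaining visits |
| QLQ-C15-PAL, EQ-5D-5L | footnote k | stop |
| Adverse events if withdrawn because of one; unresolved SAEs | 6.3.1, 8.2.3 | followed until resolved or stable |
| New related adverse events | 8.2.2, Table 2, 9.3 | stop |
| Hospitalizations | footnote i, Table 2, 9.3 | stop |

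**2. Timing of late toxicity.** Section 8.2.2 defines late toxicity as appearing more than 90 days after the last RT dose, and section 6.1.2 starts RT within 21 days of randomisation. For a single fraction on day 21, the late period begins after day 21 + 90 = 111. It is therefore essentially the visits at 6, 12, 18 and 24 months that can detect it. An arm B patient who leaves in the first three months adds no new late-toxicity data.

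**3. Who can be selected.** RT is assigned only in arm B (6.1.2), and the RT-related adverse-event category applies only there (8.1.4). Arm A has its own rule that can be broken, the bar on upfront preventive RT (5.1), and adverse events related to bone disease are recorded in both arms (8.2.2).

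**4. Planned drop-out.** Section 9.1 inflates 96 patients for 20% drop-out: 96/(1 − 0.20) = 120, as stated. That is 120 × 0.20 = 24 patients, or 12 per arm if equal. The protocol calls this drop-out non-informative and does not split it by reason or arm. The rest of this step therefore uses assumed rates.

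*Quality of life.* Let a share p of an arm leave, and let leavers score d worse than those who stay. The full-arm mean is then the stayers' mean minus p × d, so analysing stayers alone overstates the arm by p × d. The between-arm bias is (pB − pA) × d, positive in favour of arm B. With 60 per arm and d = 0.5 SD (assumed):

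| pA | pB | Observed A / B | Bias (SD) |
|---|---|---|---|
| 20% | 20% | 48 / 48 | 0 |
| 10% | 20% | 54 / 48 | 0.05 |
| 0% | 20% | 60 / 48 | 0.10 |
| 0% | 40% | 60 / 36 | 0.20 |

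The last row puts the whole planned 20% into arm B. If arm A loses more, the sign reverses.

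*Late toxicity in arm B.* Suppose 6 of 60 leave, with a late grade 2+ rate of 40% against 20% in the other 54 (all assumed). The true rate is (54 × 0.20 + 6 × 0.40)/60 = (10.8 + 2.4)/60 = 22%. The observed rate is 10.8/54 = 20% if leavers are dropped, or 10.8/60 = 18% if they are counted as event-free. The understatement is 2 to 4 percentage points.

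**5. A second loss.** Section 6.2 and footnote h separately reduce collection to survival and further SSEs after a first SSE. At the planned 2-year SSE-free survival of 20% and 45% (9.1), at most 60 × 0.20 = 12 patients in arm A and 60 × 0.45 = 27 in arm B would still be on the full schedule at 24 months. Part of that fall is death, but the rule thins arm A's quality-of-life data more than arm B's.

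**The case against.** A reader might infer that the triggers fall mainly on arm B, that its compliant patients would be compared with nearly all of arm A, and that quality of life is therefore biased in favour of upfront RT. The documents do not support this:

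- No rate by arm is given. Arm A can deviate throughout the trial, since the background section says that preventive RT is already given at the physician's choice.
- Standard conventional RT is a single fraction, which leaves little course to break off, and section 10.1.4 expects no high-grade side effects.
- The stop at a first SSE removes more arm A quality-of-life data under the trial's own assumptions.

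Nor is it right that the protocol has no place for a patient who is off RT but still followed. Section 5.3 records early termination of RT, with its reason, without ending participation, and section 10.4.4 handles deviations case by case. The list in 6.3.1 is permissive, and section 10.4.5.3 mentions a final visit for those who leave, although its content is not defined.

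The numerical effects are also modest. A 2 to 4 point shift lies within one binomial standard error of 22% in 60 patients: √(0.22 × 0.78/60) is about 5 points.

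All of this stands and limits the point. It does not remove it. Once a site uses the option, the text ends collection of three outcomes in a consenting patient, and it gives the site no criterion for when to use it.

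**Conclusion.** The point holds for the secondary endpoints. Read as written, the protocol allows adherence or tolerance to decide whether quality of life, new related toxicity and hospitalizations are observed, in patients who have not withdrawn consent. The primary endpoint and overall survival are not affected.

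The size cannot be derived from the documents. On assumed inputs the quality-of-life bias ranges from 0 to 0.20 SD in favour of arm B, or the other way if arm A loses more, and a late-toxicity rate could be understated by 2 to 4 points. RT-related triggers exist only in arm B, so understatement of RT toxicity is the firmest part, provided that those who leave have more late toxicity than those who stay. For quality of life and hospitalizations the net direction is unknown.

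The case for acting rests on the loss being selective and irrecoverable, not on a demonstrated size.

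**What to change.** - **Section 6.3.1:** separate not starting or not completing study RT from ending participation, so that a deviation, non-compliance or an adverse event alone does not end data collection.
- **Footnotes k and i, section 8.2.2, and the windows in Table 2 and section 9.3:** continue both questionnaires, related adverse events and hospitalizations to 24 months for every patient who has not withdrawn consent and can be contacted.
- **Section 4.5:** reconcile the rule that consented patients who do not start treatment are screen failures with the sentence before it, which ties withdrawal of consent to the time before treatment assignment, and with section 4.1, where assignment makes a patient enrolled. Randomised patients should stay in follow-up and analysis.
- **Section 6.3:** replace the template line with an exit assessment, using the next visit's assessments brought forward, as section 6.2 already does at an SSE.

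The cost is protocol wording, a discontinuation form with two separate items, and a few more questionnaires and adverse-event checks at timepoints where survival and SSE data are already sought. Some patients will decline. The sample size, the number of events, treatment and the right to withdraw are unchanged.

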6.3.2 Subjects lost to follow-up

A subject will be considered lost to follow-up if they fail to return for scheduled visits and are unable to be contacted by the study center.

The following actions must be taken if a subject fails to return to the study center for a required study visit:

- The study center must attempt to contact the subject and reschedule the missed visit as soon as possible. The study center must counsel the subject on the importance of maintaining the assigned visit schedule and ascertain whether the subject wishes to and/or should continue in the study.
- Before a subject is deemed lost to follow-up, the Investigator or designee must make every effort to regain contact with the subject (where possible, 3 telephone calls and, if necessary, a certified letter to the subject's last known mailing address or equivalent methods). These contact attempts should be documented in the subject's CRF.
- Should the subject continue to be unreachable, they will be considered to have withdrawn from the study.

6.4 Study termination

The sponsor reserves the right to terminate any portion of the study at any time. Possible reasons for termination include:

1. Safety reasons.
2. New scientific knowledge becomes known that makes the objectives of the study no longer feasible/valid.
3. Unsatisfactory enrollment of participants.

In terminating the study, the sponsor will ensure that adequate consideration is given to the protection of the subjects' interests.

7. Study assessments

The frequency and timing of efficacy, safety, and other measurements for subjects are presented in the Schedule of Events (SOE) (see Table 1).

7.1 Screening evaluations and measurements

Within 3 weeks prior to randomization:

7.1.1 Medical History and Prior Medications

-Medical history (including date of the initial diagnosis of the primary cancer, site and histology of the primary cancer, date of diagnosis of metastatic disease and the number of metastases at the time of the screening visit)

HERMES/CTO23032GZA – Protocol v3.0 07-OCT-2024

41/70

Clinical Trials Oncology

Ref.Nr.: P.01-S.23

Versie: 6.0

-Anticancer therapy, bone-modifying agents and pain medications (including corticoid therapy) within 7 days before screening visit will be recorded at screening.

7.1.2 Demographics

Gender, year of birth and age will be recorded as part of the screening procedures.

7.1.3 Pain assessment

As the presence of asymptomatic or minimally symptomatic high-risk bone metastase(s) is an inclusion criterion of this study, the patient's pain will be evaluated per lesion by determining the Numeric Pain Rating Scale (NRS) score. Asymptomatic or minimally symptomatic is defined as an NRS score ≤ 2 . The NRS score is explained in appendix 1 of this protocol.

7.1.4 Karnofsky Performance Score (KPS)

The KPS should be documented in the subject's medical record or study source documentation at applicable visits. A copy of the document is included in Appendix 5 (Karnofsky Performance Score Assessment) for reference.

7.1.5 High-risk bone metastase(s) characteristics: (localization, high-risk definition, number of metastases enrolled)

Based on imaging (CT, MRI or PET-CT), the characteristics of the high-risk bone metastasis(es) that is (are) asymptomatic or minimally symptomatic will be determined and captured in the eCRF, including the total number of bone metastases, the location of the high-risk bone metastases (high-risk definition) and the number of metastases enrolled.

High-risk is defined as follows:

- o Bulky site of disease in bone (diameter ≥ 2 cm)
- o Disease involving the hip (acetabulum, femoral head, femoral neck), shoulder (acromion, glenoid, humeral head), or sacroiliac joints
- o Disease in long bones with cortical involvement of $>1/3$ in proportion to the diameter of the bone (humerus, radius, ulna, clavicle, femur, tibia, fibula, metacarpals, phalanges)
- o Disease in vertebrae of the junctional spine (C1-2, C7- T1, T12-L1, L5-S1) and/or disease with posterior element involvement or epidural extension (Bilsky epidural compression score 1a-3; see appendix 7) [Bilsky et al]

Furthermore, whether metastases on other locations than the bone are present should be documented in the eCRF.

Images up to 12 weeks old at the time of randomization are allowed. If not available, screening will take place at the time repeat imaging will be performed according to the standard of care guidelines.

7.1.6 QLQ-C15-PAL questionnaire and EQ-5D-5L questionnaires

The EORTC QLQ-C15 questionnaire and the EQ-D5-5L questionnaire are used to evaluate the quality of life of the patients in both treatment arms ([see section 7.4.](#)).

7.1.7 Pregnancy test for women of child-bearing potential

Pregnancy testing (serum HCG) should be conducted at screening (within 72 hours before the randomization date) for women of child-bearing potential. Additional serum or urine pregnancy tests may be performed, as determined necessary by the Investigator or required by local regulation, to establish the absence of pregnancy at any time during the patient's participation in the study.

7.1.8. Number of Risk Factors (NRF) score

The NRF score should be documented in the subject's medical record or study source documentation during screening (see section 5.1) as it will be used to determine the RT scheme (palliative vs stereotactic dose). In addition, NRF score should be documented in the eCRF.

7.1.9. Assessment of (serious) adverse events ((S)AE) during screening

The occurrence of (S)AE as measured with NCI-CTCAE v5.0 (see appendix 4) will be documented in the eCRF (see section 8). Only (S)AE that are related to the bone metastatic disease will be documented at screening.

7.2 Efficacy Evaluations

- Comparison of the number of SSE's in both study arms. SSEs are defined as:
 - symptomatic pathological fracture
 - spinal cord compression leading to neurological deficit or pain
 - Indication for palliative radiotherapy (for bone pain, cord compression or (impending) fracture)
 - Indication for orthopedic surgery (for bone pain, cord compression or (impending) fracture)

All SSE's will be recorded in both study arms. Patients in the upfront RT arm may develop an SSE in a bone metastasis that was not previously included in the study, which also needs to be registered. An exception are SSE's in bone metastases that were already treated with surgery or RT before study participation

Patients in the upfront RT arm developing new minimally symptomatic or asymptomatic high-risk bone metastases during study participation are strongly advised to further be treated with preventive RT. Details concerning the characteristics of these new high-risk metastases as well as details regarding the preventive RT must be captured in the eCRF.

- Comparison of the number of **hospitalizations** related to the high-risk bone metastasis(es) between observation/systemic therapy and upfront RT plus observation/systemic therapy
- **Overall survival:** from time of study randomization to date of death of any cause or last follow-up visit (24m after randomization date)
- To compare **quality of life** between observational arm (arm A) and upfront RT arm (arm B), using the EORTC QLQ-C15-PAL form and the EuroQol Group EQ-5D-5L form

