2. Study objectives and endpoints

The primary and secondary objectives and endpoints of the study are presented in Table 2.

Table 2: Objectives and endpoints for the Hermes trial

Objectives	Endpoints
Primary	
To assess whether early preventive radiation of the high-risk asymptomatic or minimally symptomatic bone metastases in patients with metastatic cancer can decrease the number of SSEs*.	
 Time to a symptomatic skeletal related event (SSE) in any bone metastasis or death due to any cause.
Secondary	

 To evaluate the need for hospitalization related to the high-risk bone metastase(s) To assess overall survival (OS) To evaluate quality of life (QoL) 	
 The number of hospitalizations related to the high-risk bone metastases will be compared between systemic therapy/observation (arm A) and upfront RT (arm B) from date of study randomization to last follow-up visit (24m after randomization date), date of death of any cause or early end of participation in the study due to other reasons Overall survival will be assessed from time of study randomization to date of death of any cause or last follow-up visit (24m after randomization date) Quality of life will be compared between systemic therapy/observation (arm A) and upfront RT (arm B),

 To evaluate acute and late toxicity 	
using the EORTC QLQ-C15-PAL questionnaire (see appendix 2) and the EuroQol Group EQ-5D-5L questionnaire (see appendix 3)
 
 Adverse events in both study arms will be evaluated using the National Cancer Institute Common Terminology Criteria for Adverse Events (NCI-CTCAE) v5.0 (see appendix 4) from the time of ICF signing to last follow-up visit (24m after randomization date), date of death of any cause or early end of participation in the study due to other reasons. Only adverse events that are related to the bone metastatic disease or related to the radiotherapy (only for patients in arm B) will be reported in the eCRF.
---	--

*SSEs are defined as:

- symptomatic pathological fracture
- spinal cord compression leading to neurological deficit or pain
- Indication for palliative radiotherapy (for bone pain, cord compression or (impending) fracture)
- Indication for orthopedic surgery (for bone pain, cord compression or (impending) fracture)

3. Overall study design.

[figure not shown]

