4.2 Subject inclusion criteria

To be included in this study, each subject must satisfy all the following criteria:

- Histologically **confirmed solid tumor malignancy** (with polymetastatic spread (more than 3 metastases))
- **High-risk bone metastasis(es)** that is (are) asymptomatic or minimally symptomatic [Rosen et al]:
 - Asymptomatic or minimally symptomatic is defined as follows:
 - Numeric Pain Rating Scale (NRS) score ≤ 2 for the specific lesion(s) (see appendix 1)
 - High-risk is defined as follows:
 - Bulky site of disease in bone (diameter ≥ 2 cm)
 - Disease involving the hip (acetabulum, femoral head, femoral neck), shoulder (acromion, glenoid, humeral head), or sacroiliac joints
 - Disease in long bones with cortical involvement of $>1/3$ in proportion to the diameter of the bone (humerus, radius, ulna, clavicle, femur, tibia, fibula, metacarpals, phalanges)
 - Disease in vertebrae of the junctional spine (C1-2, C7- T1, T12-L1, L5-S1) and/or disease with posterior element involvement or epidural extension (Bilsky epidural

compression score 1a-3; see appendix 7) [Bilsky et al]. The posterior elements of the spine consist of the pedicles, laminae, facets (articular processes), transverse processes, and the spinous process.

- Number of Risk Factors (NRF) prognostic score 0-2 (see section 5.1)
- Age \geq 18 years
- Ability to provide informed consent (either by the patient or by a LAR)
- A female participant is eligible to participate if she is not pregnant, and one of the following conditions applies:
Is not a woman of child bearing potential or

A woman of child bearing potential must have a negative serum pregnancy test at screening (see section 7.1.7) and must use a very effective method of birth control

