5.1 Description

Patients will be randomized (1:1) to receive either systemic therapy/observation (Arm A) or early RT plus systemic therapy / observation (Arm B).

Arm A:

The observational arm (Arm A) will include **observation or systemic therapy**, according to the treating physician's discretion. Systemic therapy may include continuation of the current systemic therapy or initiation of a new systemic therapy.

These patients will be able to receive palliative RT to progressed, painful lesions (an SSE) only at the time of symptom worsening (NRS > 2/10 or need for opioids) or determination of spinal cord compression with neurological symptoms or (high risk for) fracture requiring surgical intervention. Upfront preventive RT is not allowed.

Arm B:

The intervention in this study is **early, upfront radiation therapy** to asymptomatic or minimally symptomatic (defined as high-risk) bone metastases. Up to 5 high-risk asymptomatic or minimally symptomatic metastatic locations per patient are allowed.

The radiotherapy (RT) doses used will be in accordance with common practice palliative RT schedules. As such a single fraction of 8 Gy is considered for all patients, except for patients with a very good prognosis (NRF prognostic score 0-1) in which a higher dose will be used with SABR [Chow et al].

Table 3: Predictive model for estimation of median overall survival (OS): NRF-model [Chow et al].

Three variables:

- **Primary cancer type** -> risk factor: non breast/prostate/lung cancer
- **Site of metastases** -> risk factor: metastases other than bone
- **Karnofsky performance score (KPS)** -> risk factor: KPS ≤60

0-1 risk factors	median OS 64 weeks	95%CI: 37-undefined
2 risk factors	median OS 28 weeks	95% CI 22-34
3 risk factors	median OS 10 weeks	95% CI 8-13

Simulation:

All patients will be immobilized in a comfortable and stable position to irradiate the metastatic lesion(s). Support and/or immobilization devices will be used to increase patient comfort or to ensure set-up reproducibility. A planning CT scan will be acquired without intravenous contrast with <3mm CT slice thickness (1mm for SABR) encompassing the region of interest with sufficient margin for treatment planning, a typical scan length should extend at least 10 cm superior and inferior beyond the treatment field borders. The isocenter will be placed in the middle of the affected bone lesion.

Target volume definition:

1. *Conventional radiotherapy:*

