9.1 Justification of sample size

In collaboration with statistical experts UGent a sample size calculation was performed. A hazard ratio of 0.5 is deemed clinically relevant, increasing the estimated 2-year SSE free survival from 20% to 45%. Assuming exponentially distributed SSE-free survival, setting alpha to 0.05 and the required power to 0.8 and assumed non-informative drop out to 20%, this results in a sample size of 120 (96 without drop out) with a required number of events of 65.

Hazard ratio (HR) = 0.5 is in between previously observed effect sizes in similar settings: Different trials analyzing the use of bone modifying agents with the presence of SREs, showing a HR around 0.7 [Smith et al; O’Carrigan et al; Rosen et al]]. In the above-mentioned phase II trial [Rosen et al] there was a large reduction in SREs from incidence from 29% to 1.6% at 1 year in the RT group. Because in our trial SSEs and not SREs will be analyzed, we expect a more conservative HR. This was also demonstrated in a trial comparing skeletal-related events with symptomatic skeletal events for two different bone modifying agents [Smith et al].

A sample size of 96 patients was calculated to have an 80% power and an $\alpha < 0.05$. With an estimated dropout of 20%, the **total sample size will be 120** with a required number of events of 65.

Each patient will be stratified by their prognostic class (0-1 vs 2), high-risk disease location (spine location vs. other) and bone modifying agents (yes vs. no) in this hierarchical order. With 3 stratification factors for randomization, there are 8 strata, which is rather high for only 60 patients per arm. Strata where only 1 arm is present and the events in these strata, are implicitly ignored in the estimation/testing. Strata with less than 10 patients will be merged with the corresponding stratum with the same value for factor A and B, but different value for C in the upfront decided hierarchical order (cfr above).

Randomization will be completed on a per patient basis (not lesion based), even though each patient may have up to 5 multiple sites of metastatic bony disease.

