Appendix 7: ESCC grading score [Bilsky et al]

Schematic representation of the 6-point ESCC grading scale.

Grade 0: bone-only disease;

Grade 1a: epidural impingement, without deformation of the thecal sac;

[figure not shown]

Grade 1b: deformation of the thecal sac, without spinal cord abutment;

Grade 1c: deformation of the thecal sac with spinal cord abutment, but without cord compression;

Grade 2: spinal cord compression, but with cerebrospinal fluid (CSF) visible around the cord;

Grade 3: spinal cord compression, no CSF visible around the cord.

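### An indication for palliative RT or surgery already present at randomisation in a non-enrolled bone lesion can count as a primary event near day 0, pulling the hazard ratio towards 1

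*Protocol*

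**What the plan says.** - **Entry.** Protocol 4.2 requires more than three metastases and an NRS pain score of 2 or less, but the score applies "for the specific lesion(s"). The exclusions in 4.3 remove a lesion with a pathological fracture or with an impending one at Mirels 9 or more. They do not remove a patient who has another painful, untreated bone metastasis.
- **Endpoint.** Section 9.3 times the first SSE, in whichever bone metastasis it arises, or death, from the date of randomisation.
- **SSE list.** Sections 2 and 7.2 give four components. One is "Indication for palliative radiotherapy (for bone pain, cord compression or (impending) fracture"). What counts is the indication, not delivered treatment, and the list does not say that it must be new.
- **Exception.** Section 7.2 and footnote j of Table 1 leave out only SSEs in "bone metastases that were already treated with surgery or RT before study participation".
- **Arm A access to palliative radiotherapy.** Section 5.1 allows it "only at the time of symptom worsening (NRS > 2/10 or need for opioids"), among other triggers. Arm B has no matching text.
- **Epidural disease.** Bilsky grades 1a to 3 are eligible under 4.2. Appendix 7 defines "Grade 2: spinal cord compression, but with cerebrospinal fluid (CSF) visible around the cord", and grade 3 is also cord compression.

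**The concern.** Take a patient with one enrolled painless lesion and a second, non-enrolled bone lesion that already hurts and has a standing indication for radiotherapy. The patient is eligible. The second lesion has not been treated, so the exception does not reach it. Read as written, the indication is an SSE as soon as the clock starts.

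Such an event is prevalent, not incident, and upfront radiotherapy to the enrolled lesion cannot affect it. It uses up the patient's time-to-first-event outcome. Under footnote h and section 6.2, once the SSE assessments are done only survival and further SSEs are recorded, so later quality-of-life data are lost as well. Events of this kind fall equally in both arms and carry no information on the treatment effect, so they pull the hazard ratio towards 1.

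The trial is open-label (5.2), so whether a site registers such a condition is a judgement made with the allocation known. Footnote j adds to the doubt: it labels SSEs in lesions not included in the study as applicable to arm B only, while 9.3 makes no such distinction between arms.

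**Working it through.** **Inputs from section 9.1.** "setting alpha to 0.05 and the required power to 0.8"; "A hazard ratio of 0.5 is deemed clinically relevant"; 2-year SSE-free survival of 20% against 45%; 96 patients, 120 with 20% dropout; 65 events. Follow-up is 24 months per patient (3.2.1). The sidedness of alpha is not stated, but two-sided reproduces the plan.

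**Step 1: the plan's own figures.**
- Events by Schoenfeld: 4 × (1.960 + 0.842)² / (ln 0.5)² = 65.3, against 65 stated.
- Mean 2-year event probability: (0.80 + 0.55) / 2 = 0.675. Patients: 65 / 0.675 = 96.3, against 96 stated.
- With dropout: 96 / (1 − 0.20) = 120, as stated.

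**Step 2: add day-0 events.** Let a share f of patients in each arm have a qualifying condition at randomisation. The protocol gives no value for f, so every value below is an assumption. The simulation used 10,000 trials per value, 96 patients, exponential times with 20% control survival at 24 months (hazard ln 5 / 24 = 0.067 per month), a true hazard ratio of 0.5, a Cox estimate and an unstratified log-rank test.

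| f, both arms | Hazard ratio | Power | Mean events |
|---|---|---|---|
| 0% | 0.50 | 79% | 65.0 |
| 5% | 0.52 | 75% | 66.5 |
| 10% | 0.55 | 69% | 68.1 |
| 20% | 0.60 | 56% | 71.2 |
| 30% | 0.65 | 43% | 74.3 |

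**Step 3: check by hand at f = 10%.**
- Day-0 events: 96 × 0.10 = 9.6, with an expected log hazard ratio of 0.
- Remaining events: 86.4 × 0.676 = 58.4, with log hazard ratio ln 0.5 = −0.693. (0.676 is the mean of 0.80 and 1 − √0.20 = 0.553, the exact value under a hazard ratio of 0.5.)
- Total: 68.0. Weighted log hazard ratio: (58.4 / 68.0) × (−0.693) = −0.595, so the hazard ratio is 0.55.
- Power: √(68.0 / 4) × 0.595 − 1.96 = 0.49, which gives 69%.

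The hand figures agree with the simulation. The total number of events rises with f, so the blinded look at the event rate in 9.4 would not flag the problem from that rate alone.

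**Step 4: a condition in an enrolled lesion.** Arm B irradiates that lesion upfront, so a baseline indication there would be counted mainly in arm A. With f in arm A only, the simulated hazard ratio is 0.47 at 5%, 0.44 at 10% and 0.40 at 20%. The effect is exaggerated, not diluted.

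**The case against.** The strongest reply is that incidence is implied. Section 9.3 times the occurrence of an SSE from randomisation, footnote h speaks of events during the study, and 5.1 ties arm A's palliative radiotherapy to worsening. Baseline fractures are excluded, and 4.1 has the investigator judge whether a patient is a suitable candidate. This lowers the likely frequency, but it does not settle the rule. The worsening text governs access to radiotherapy in arm A only, and no such wording stands in the SSE list.

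It is also fair that the size rests on an unknown prevalence. Nothing in the protocol supports 20% or 30%, and at 5% the loss is about four points of power.

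A reader might infer more than the text supports:
- **Cord compression seen on imaging alone is an SSE at entry.** It is not. The cord-compression component requires neurological deficit or pain. What remains is narrower: for an enrolled lesion at Bilsky grade 2 or 3, the radiotherapy-indication component names cord compression without saying that the indication must be new.
- **Opioid use at entry is already an SSE.** It is not one of the four components. It appears in 5.1 under worsening, and a patient on a stable opioid has not worsened.
- **Every baseline condition dilutes the effect.** Step 4 shows the opposite direction for enrolled lesions, so the equal-share table does not describe them.

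**Conclusion.** The concern holds for non-enrolled, untreated bone lesions that are painful or already have an indication for palliative radiotherapy or surgery at randomisation. Such patients are eligible, the exception does not cover the lesion, and the endpoint as written can date an event near day 0 in either arm. With both arms equally affected, each of the assumed shares moves the hazard ratio towards 1. At 10% it is about 0.55 with 69% power, against 0.50 and 79% if these conditions are not counted. The figures assume 96 evaluable patients, exponential times and events at essentially day 0.

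The enrolled-lesion case (Bilsky grade 2 or 3) is secondary and runs the other way, towards an exaggerated benefit. Both have the same cause: the SSE list does not require that an indication be new. The protocol should be changed, but the finding does not extend to opioid use or imaging-only compression as events in themselves.

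**What to change.** Change the counting rule only, identically in both arms:
1. In 7.2, Table 1 footnote j and 9.3, state that an SSE must be a new event or a new indication arising after randomisation.
2. Extend the existing exception to an indication for radiotherapy or surgery that is already present at randomisation. Except the indication, not the lesion: a later new fracture, cord compression or new indication in the same lesion still counts.
3. Before randomisation, record in the eCRF any non-enrolled bone lesion that is symptomatic (NRS above 2) or already has such an indication.
4. Reconcile footnote j, 5.1, 7.2 and 9.3 on which lesions count in which arm and on whether worsening is required. How these patients are treated is not at issue here.

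The rule needs no per-lesion pain score during follow-up, which Table 1 schedules at screening only. The cost is a short extra screening item, because 7.1.5 details only the high-risk lesions and otherwise asks for a total count of bone metastases. There would also be slightly fewer countable events: at f = 10%, about 65 instead of 68, which still matches the planned 65 under the plan's own assumptions.
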